3.2.6 Immunogenicity Samples

3.2.6.1 Immunogenicity Sample for Human SNA Assay

Chikungunya virus SNA levels will be assessed using a validated human SNA assay that measures NT₈₀ titer. Blood (serum) samples will be taken on Day 1 (prior to IP administration), Day 15, Day 22, and Day 183 End of Study Visit (or at Early Discontinuation/Withdrawal).

For additional information on sample collection, processing, storage, shipment, and retention refer to the study Laboratory Manual.

3.2.6.2 Immunogenicity Sample for Various CHIKV Genotypes

Neutralizing antibodies against various CHIKV genotypes will be measured for a subset of participants in the PXVX0317 group using FRNT50. Blood (serum) samples will be collected on Day 1, Day 22, and Day 183 End of Study Visit.

3.2.7 Investigational Product Administration

Investigational product is 0.8 mL in volume and administered by IM injection into the deltoid muscle with a pre-filled syringe attached to 25 gauge 1" (or 1.5") needle, using universal precautions and sterile technique in accordance with General Best Practice Guidelines for Immunization: Best Practices Guidance of the Advisory Committee on Immunization Practices (ACIP) (20) per [Table 2](#). Investigational product is to be administered only under the direct supervision of the investigator or a qualified subinvestigator identified on the FDA Form 1572.

Table 2 Needle Length and Injection Site of Intramuscular Injections for Adults ≥ 19 Years of Age (by Sex and Weight)

Sex, Weight	Needle length	Injection Site	
Men and women, <60 kg (<130 lbs)	1 inch (25 mm) ¹	Deltoid muscle of arm	
Men and women, 60–70 kg (130–152 lbs)	1 inch (25 mm)		
Men, 70–118 kg (152–260 lbs)	1–1.5 inches (25–38 mm)		
Women, 70–90 kg (152–200 lbs)			
Men, >118 kg (260 lbs)	1.5 inches (38 mm)		
Women, >90 kg (200 lbs)			

Source: Adapted from Table 6-2, General Best Practice Guidelines for Immunization: Best Practices Guidance of the Advisory Committee on Immunization Practices (ACIP) (20).

¹Some experts recommend a 5/8-inch needle for men and women who weigh <60 kg, if used, skin must be stretched tightly (do not bunch subcutaneous tissue).

Under no circumstances will the investigator allow PXVX0317 vaccine to be used other than as specified in the protocol.

For further details on the IP refer to Section 5.1.

3.2.8 Acute Observation After Investigational Product Administration

The participant will be monitored by study staff for signs of an acute adverse reaction for at least 30 minutes after injection and vital signs will be obtained 30 minutes to one hour after vaccination.

3.2.9 Assess Solicited Adverse Events

Electronic or paper diaries (memory aids) will be used to collect solicited AEs following vaccination. Participants will record events in their diary daily, for at least seven days after vaccination. Solicited AEs to be assessed in this study are local events of pain, redness, and swelling at the injection site and systemic events of oral temperature $\geq 38.0^{\circ}\text{C}$ ($\geq 100.4^{\circ}\text{F}$), chills, fatigue, headache, myalgia, arthralgia, and nausea.

Participants will be trained to complete a diary (electronic or paper) to observe, measure, and record these solicited AEs daily. A digital thermometer will be provided to the participants to measure their temperature each day. The highest temperature measured each day should be recorded in the participant's diary or memory aid (electronic or paper). To record injection site local reactions, a ruler will be provided to the participant to measure and record the diameter of redness and swelling at the largest point of the reaction each day.

Study staff will review the signs and symptoms recorded in the diary or memory aid (electronic or paper) daily and will follow-up with participants if any data is missing. The investigator will then assess all solicited AEs for severity (Section 8.1.8) and the action taken, and causality (Section 8.1.9). The results of the investigator's assessment will be recorded as a separate source document and will be entered on the solicited AE eCRF.

Symptoms continuing beyond the solicited AE collection period will be collected and recorded on the AE eCRF.

Details on safety definition, evaluation, reporting periods and documentation are outlined in Section 8.

3.2.10 Assess Unsolicited Adverse Events

Unsolicited AEs (AEs not listed in the diary or memory aid [electronic or paper]) will be collected from Day 1 through 28 days post vaccination.

Details on safety definition, evaluation, reporting periods and documentation are outlined in Section 8.

3.2.11 Assess Serious Adverse Events, Medically Attended Adverse Events, and Adverse Events of Special Interest

Serious Adverse Events, AESI, and MAAE will be collected for all participants from Day 1 through Day 183 End of Study Visit.

Details on safety definition, evaluation, reporting periods, and documentation are outlined in Section 8.

3.3 Study Endpoints

3.3.1 Primary Endpoints

Coprimary Immunogenicity Endpoints

- Difference in anti-CHIKV SNA seroresponse rate (PXVX0317 minus placebo) and associated 95% CI at Day 22.
Success criterion: Lower bound of the two-sided 95% CI on the difference in seroresponse rates between PXVX0317 and placebo groups █ (equivalent to a difference >0 using a two-sided chi-square test).
- Anti-CHIKV SNA GMT and associated 95% CIs at Day 22 for PXVX0317 and placebo.
Success criterion: Significant difference in the IEP across all age groups combined using an ANOVA model with logarithmically transformed anti-CHIKV SNA titers (\log_{10}) as the dependent variable and treatment group and study site as the fixed effects with a two-sided significance level of 0.05.

Note: Seroresponse rate (considered the presumptive seroprotection rate) is defined as the percentage of participants who achieve an anti-CHIK SNA █. See Section 9.6.2 for immunogenicity analysis details and Section 9.4 for success criteria and multiplicity controls.

Safety Endpoints

- Incidence of solicited AEs through Day 8 for PXVX0317 and placebo.
- Incidence of unsolicited AEs through Day 29 for PXVX0317 and placebo.
- Incidence of SAEs, MAAEs, and AESI through Day 183 for PXVX0317 and placebo.

3.3.2 Secondary Immunogenicity Endpoints

- **Key Secondary Immunogenicity Endpoints:** Difference in anti-CHIKV SNA seroresponse rate (PXVX0317 minus placebo) with associated 95% CIs at Day 15 and Day 183, in that order (see Section [9.6.2](#)).
- Anti-CHIKV SNA GMTs by study arm with associated 95% CIs at Day 15 and Day 183.
- Geometric mean fold increase from Day 1 to subsequent collection time points.
- Number and percentage of participants with an anti-CHIKV SNA titer ≥ 15 and 4-fold rise over baseline.

3.3.3 Exploratory Immunogenicity Endpoint

Geometric mean titers and associated two-sided 95% CIs for neutralizing antibodies against various CHIKV genotypes measured at Day 22 (and at baseline if necessary) for a subset of participants in the PXVX0317 group.

3.4 Measures Taken to Minimize/Avoid Bias

3.4.1 Masking/Blinding Procedures

Study participants, the investigator, and study site personnel will remain blinded to all randomization assignments throughout the study. Sponsor's MM and personnel, who are in regular contact with the study site and/or involved with documentation associated with the study will remain blinded to all participant randomization assignments.

The following safeguards will be employed to reduce the risk of inadvertent unblinding:

- Use of a standardized pre-filled syringe and injection volume for all injections.
- All PXVX0317 and placebo syringes have a semi-transparent barrel cover to mask any difference in appearance between placebo and PXVX0317.
- No sponsor personnel will have access to the randomization schedule. No site personnel will have access to treatment assignments. The Randomization and Trial Supply Management (RTSM) system allows for unblinding in an emergency (see Section [3.4.1.1](#)).

- Assays will be run in a blinded manner. The assay titer results will not be delivered to the sponsor data management and analysis teams until after database lock, as they are potentially unblinding.
- Should any participant or staff member become inadvertently unblinded, the investigator will promptly (within 24 hours of their awareness of the error) disclose the event to the sponsor's MM in a blinded fashion (disclosing only participant number, not treatment) so that corrective action can be initiated. The unblinding sequence of events will be documented and retained as source documents. A protocol deviation will be entered in the eCRF.

Members of the SMC may have access to unblinded data as defined in the SMC Charter for safety/other data review.

Under certain circumstances (eg, safety reasons, required reporting to regulatory agencies), unblinding of IP for a particular participant will be allowed. This safety unblinding will be documented as a protocol deviation. Otherwise, unblinding of the study will only occur after the clinical database has been locked.

Refer to the Pharmacy Manual for procedures in case of accidental unblinding of study-affiliated personnel.

3.4.1.1 Breaking the Blind for Individual Participants

If the PI determines that knowledge of a participant's treatment assignment is urgently needed to guide treatment or ensure the participant's safety, the PI may perform emergency unblinding via the RTSM system. The PI must attempt to notify the sponsor MM prior to unblinding and must notify the sponsor MM within 24 hours after unblinding at the latest.

If a participant's study treatment assignment is unblinded for safety reasons, or if a participant becomes accidentally unblinded for any reason, the participant will be requested to remain in the study for safety follow-up.

Documentation of breaking the blind must be entered in the study participants' source documents with the following information recorded: (i) date and time the blind was broken; (ii) the rationale behind the unblinding decision/occurrence; (iii) the names of the personnel involved; and (iv) date of contact with the sponsor MM(s). The unblinding will be documented as a protocol deviation.

3.4.2 Treatment Assignment/Randomization

Participant eligibility will be confirmed and documented by the investigator immediately prior to randomization of each participant on Day 1. Study staff will indicate on a randomization eCRF within the EDC system that they want to generate a randomization number for the participant. When they agree to proceed, a randomization number will be generated from the EDC randomization module but hidden from study staff. The EDC randomization module will match the randomization number to an IP kit available at the site

and inform the study staff of the assigned kit. Study staff will use the appropriate kit for planned administration to the participant.

Participants will be considered enrolled once a randomization number has been assigned within the EDC system. Participants will be stratified by age subgroups (65 to <75 years and ≥75 years of age), with a target of 25% enrollment of participants ≥75 years of age.

Participants will be randomized to PXVX0317 or placebo in a 1:1 ratio.

The study will be conducted as a double-blind study through Day 183 End of Study Visit. Neither participants nor clinical site personnel, including the PI, nor the sponsor will know participants' individual treatment assignments until all participants have either prematurely discontinued or completed their participation in the study through the Day 183 End of Study Visit and the database has been cleaned and locked.

3.5 Description of Stopping Rules

There are no specific predefined stopping rules for this study; however, an independent SMC will provide safety oversight. The SMC will review aggregated, blinded safety data after the first 50 participants have completed seven days of safety follow-up. The remaining participants will be enrolled following the safety review by the SMC and based on the sponsor's consideration of the SMC's recommendation. The need for any further reviews will be determined by the SMC.

3.6 Accountability Procedures

The PI (or designee) is responsible for maintaining accurate inventory records of the IP and placebo.

3.7 Maintenance of Study Intervention Randomization

Please see Section [3.4](#).

3.8 Data Directly Recorded on the Electronic Case Report Form

Data recorded directly from the e-Diary will be considered source data.

3.9 End of Study

A participant is considered to have completed this study if he/she has been dosed with IP and completed the final planned study visit at Day 183. Participants who do not complete the Day 183 visit are considered to have been withdrawn from the study. For participants that terminate early, efforts should be made to conduct an EDV.

The End of Study Date is defined as the date of the participant's last study visit on Day 183 or EDV.

3.9.1 Terminating the Study

The sponsor reserves the right to stop or terminate the study at any time for clinical or administrative reasons.

Any decision to voluntarily suspend or terminate a clinical study will be carefully reviewed and fully justified. The sponsor will notify the applicable regulatory authority of any suspension or termination, along with justification for terminating the study.

The sponsor will notify the investigators, FDA, and central institutional review board (IRB) of study's completion or early termination. The investigators will notify local IRBs in writing of the study's completion or early termination. The sponsor must receive a copy of the notification letter from the IRB indicating receipt of the completion or early termination letter.

3.9.2 Terminating the Study at an Individual Investigational Site

An investigational site may be terminated from the study at the discretion of the sponsor or IRB for reasons such as noncompliance, lack of recruitment, fraud or blacklisting by the regulatory authorities, relocation of the investigator, etc.

The sponsor may decide to replace a terminated investigational site.

4 SELECTION AND WITHDRAWAL OF PARTICIPANTS

4.1 Inclusion Criteria

Participants must meet all the following criteria to be enrolled:

1. Able and willing to provide informed consent voluntarily signed by participant. Must verbalize understanding of the general procedures of, and reason for the study.
2. Males or females, ≥ 65 years of age.
3. Able to complete all scheduled visits and comply with all study procedures.
4. Women who are not of CBP: surgically sterile (at least six weeks post bilateral tubal ligation, bilateral oophorectomy or hysterectomy); or postmenopausal (defined as a history of ≥ 12 consecutive months without menses prior to randomization in the absence of other pathologic or physiologic causes, following cessation of exogenous post menopausal sex-hormonal treatment).
5. Participants must be in stable health in the opinion of the investigator for at least 30 days prior to screening (eg, no hospital admission for acute illness in the last 30 days prior to screening).

4.2 Exclusion Criteria

Participants who meet any of the following criteria cannot be enrolled:

1. Participation or planned participation in an investigational clinical trial (eg, vaccine, drug, medical device, or medical procedure) within 30 days of Day 1 and for the duration of the study. **Note:** Participation in an observational trial or follow-up phase of a trial may be allowed; however, these instances should be discussed with the sponsor's MM prior to enrollment.
2. Prior receipt of any CHIKV vaccine.
3. Positive laboratory evidence of current infection with HIV, HCV, or HBV.
4. Body Mass Index $\geq 35 \text{ kg/m}^2$.
5. History of any known or suspected allergy or history of anaphylaxis to any component of the IP.
6. History of any known congenital or acquired immunodeficiency or immunosuppressive condition that could impact response to vaccination (eg, leukemia, lymphoma, malignancy, functional or anatomic asplenia, alcoholic cirrhosis). **Note:** History of basal cell and squamous cell carcinoma of the skin or carcinoma *in situ* of the cervix considered cured would not be exclusionary. History of a malignancy considered cured from over five years from the date of screening with minimal risk of recurrence is not exclusionary.
7. Prior or anticipated use of systemic immunomodulatory or immunosuppressive medications from six months prior to screening through Day 22. **Note:** For systemic corticosteroid use at a dose or equivalent dose of 20 mg of prednisone daily for 14 days or more within 90 days of screening through Day 22 is exclusionary. The use of inhaled, intranasal, topical, or ocular steroids is allowed.
8. Bleeding disorder or receipt of anticoagulants in the 21 days prior to screening, contraindicating IM vaccination, as judged by the investigator.
9. Moderate or severe acute illness with or without fever (oral temperature $\geq 100.4^{\circ}\text{F}$ [$\geq 38.0^{\circ}\text{C}$]).
10. Receipt or anticipated receipt of immunoglobulin from 180 days prior to screening through Day 22.
11. Medical condition (such as dementia) that, in the opinion of the investigator, could adversely impact the participant's participation in or conduct of the study.
12. Evidence of substance abuse that, in the opinion of the investigator, could adversely impact the participant's participation in or conduct of the study.
13. Identified as an investigator or employee of an investigator or study center with direct involvement in the proposed study, or identified as an immediate family member (ie, parent, spouse) of the investigator or employee with direct involvement in the proposed study.

14. Receipt or anticipated receipt of any vaccine from 30 days prior to Day 1 through Day 22.
15. Receipt or anticipated receipt of blood or blood-derived products from 90 days prior to screening through Day 22.
16. Any planned elective surgery that may interfere with study participation or conduct.
17. Any other medical condition that, in the opinion of the investigator, could adversely impact the participant's participation in or conduct of the study.

Reasons for Delay of Study Vaccination:

- i. Any fever (oral temperature $\geq 100.4^{\circ}\text{F}$ [$\geq 38.0^{\circ}\text{C}$]) within 24 hours of planned study vaccination.
- ii. Any condition that may interfere with assessment of reactogenicity and/or other safety assessments.
- iii. Signs and/or symptoms of an acute infectious illness.
- iv. Participants should not be randomized if they have tested positive for COVID-19 (using any type of test, even if asymptomatic) for 14 days or until negative molecular test result eg, PCR.

If any one of these occur at the time of the scheduled study vaccination, randomization is permitted later, if within the screening window (30 days), at the discretion of the investigator and after consultation with the MM. If randomization and vaccination cannot occur within the allowed screening window, rescreening will be required.

4.3 Participant Withdrawal Criteria

The participants must be available, without coercion, for all parts of the study. If continued participation jeopardizes the participant's health, the participant should be withdrawn from the study. The investigator is encouraged to consult the sponsor prior to the withdrawal of any participant, except in the event of a medical emergency. The reason for withdrawal of any participant must be clearly documented on the study source documents and the appropriate eCRF.

All participants have the right to withdraw at any time during the study without prejudice.

4.3.1 Withdrawal of Consent

All participants are free to withdraw from participation in this study at any time, for any reason, specified or unspecified, and without penalty or loss of benefits to which the participant is otherwise entitled. The investigator will ask (but cannot require) such participants to provide the reason(s) for withdrawal of consent.

For information on safety follow-up for withdrawn participants see Section [4.3.3](#).

4.3.2 Investigator-based Participant Withdrawal

The investigator may withdraw a participant from further participation in the study, at their discretion, if medically necessary or for reasons of noncompliance. The reason for withdrawal of any participant must be clearly documented on the study source documents and the appropriate eCRF. The investigator is encouraged to consult the sponsor prior to the withdrawal of any participant, except in the event of a medical emergency.

The investigator (and/or sponsor) may withdraw a participant from the study for any of, but not limited to, the following reasons:

- Noncompliance with the protocol. If the participant is noncompliant with protocol requirement, the issue should be discussed with the participant and, if not resolved, consideration given to withdrawing the participant.
- Lost to follow-up (LTF); requires documentation of at least three unsuccessful attempts to contact participants, one of which must be a registered letter. Lost to follow-up will be determined after the date of the participant's projected last visit. Study disposition date will be the last date of contact with the participant prior to LTF.
- Other reason(s) which, in the opinion of the investigator, indicates that continued participation in the study is not in the best interest of the participant.

Safety follow-up for AEs should occur for all participants. For information on safety follow-up for withdrawn participants see Section [4.3.3](#).

Reasons for withdrawal of individual participants from the study prior to the final protocol required visit and/or final safety follow-up are to be recorded on the eCRF and participant source documents.

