4.3.3 Follow-up for Withdrawn Participants

Outreach will be made to ensure that participants who are withdrawn, or who withdraw from the study, during the active observation or follow-up period will complete all safety and available assessments for the EDV as outlined in this protocol. The investigator should inform the participant that these assessments are for their own well-being and, if possible, for study purposes. The participant must first agree to the collection of early withdrawal and safety assessments prior to the assessments, and this agreement must be documented in the source documents. Additional information regarding ongoing AEs may be provided as a follow-up report.

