4.3.5 Documentation of Withdrawal

Reasons for withdrawal of individual participants from the study prior to final protocol required visit and/or safety follow-up are to be recorded on the eCRF. The reason for withdrawal from the study will be recorded as one of the following:

- Lost to follow-up (**Note:** requires documentation of at least three unsuccessful attempts to contact participants, LTF will be determined after the date of the participant's projected last visit)
- Adverse event
- Death
- Physician (ie, investigator) decision
- Other

Safety follow-up for AEs should occur for all participants, for information on safety follow-up for withdrawn participants see Section [4.3.3](#).

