8.4.2 Follow-up of Serious Adverse Events or Adverse Events of Special Interest

This study requires that participants be monitored for SAE/AESI up to Day 183 End of Study Visit.

The PI will provide or arrange appropriate care for participants for whom SAEs or a potential AESI are experienced. Withdrawal of participants from the study to treat SAEs/AESI is at the discretion of the treating PI. See Section [4.3](#) Participant Withdrawal Criteria.

All SAEs/AESI will be followed by the PI until at least one of the following conditions is met:

- The SAE/AESI is resolved or stable if expected to remain chronic.
- The participant is referred to a specialist or other physician for treatment and follow-up. The PI (or designee) will follow the participant’s condition even if the participant is seen by another physician, to obtain information about the diagnosis and outcome and any treatments and medications administered for the event.

The following will be considered acceptable reasons for discontinuation of follow-up of ongoing SAEs/AESI:

- Participant withdraws consent
- Participant is referred to appropriate long-term medical care
- Participant is considered LTF

It is expected that the investigational site will obtain supporting medical records from appropriate physicians and record this information on the SAE/AESI Report Form and AE eCRF. Additional information received related to any SAE/AESI must be forwarded within 24 hours of awareness to the Emergent Global Pharmacovigilance Department.

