9.6.3 Investigational Product Administration and Treatment Compliance

Investigational product administration data will be summarized for the randomized population and listed by participant.

Treatment compliance is not applicable since this study involves a single, in-clinic IP administration.

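### After withdrawal for noncompliance, a dosed participant has no scheduled safety follow-up to Day 183, and the unobserved time counts as event-free

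*Protocol*

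**What the plan says.** **Permission to withdraw.** Protocol 4.3.2: "The investigator may withdraw a participant from further participation in the study, at their discretion, if medically necessary or for reasons of noncompliance". The list that follows is open and also gives the power to the sponsor: "The investigator (and/or sponsor) may withdraw a participant from the study for any of, but not limited to, the following reasons". Noncompliance is to be discussed with the participant first, and withdrawal considered if it is not resolved. Nothing separates the time before dosing from the time after it. Protocol 9.6.3: "Treatment compliance is not applicable since this study involves a single, in-clinic IP administration".

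**What follows withdrawal.** Section 4.3.2 says that AE follow-up should be done for everyone and refers to 4.3.3. There the means is outreach so that withdrawn participants "will complete all safety and available assessments for the EDV as outlined in this protocol", subject to their agreement. Section 6.7 maps the EDV to the schedule of Visit 3, 4 or 7 according to its timing. Section 3.9 makes the EDV that person's end-of-study date. Section 8.4 follows events until they resolve or stabilize, or up to 30 days after the last visit.

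**What the endpoint needs.** Protocol 3.3.1 lists "Incidence of SAEs, MAAEs, and AESI through Day 183 for PXVX0317 and placebo". Section 3.2.11 has these events collected from every participant through Day 183.

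**How it is analyzed.** SAP 5.3 keeps in the safety population nearly everyone who was dosed. SAP 9.2.1 reports counts and percentages.

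**How withdrawal is coded.** Protocol 4.3.5: "The reason for withdrawal from the study will be recorded as one of the following". The list is loss to follow-up, adverse event, death, physician decision and other.

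**The concern.** With one injection on Day 1, there is no later treatment for a noncompliant participant to stop. Noncompliance after that can only concern visits, samples, diaries or prohibited products. The plan already handles these: SAP 5.2.1 gives them as examples of important deviations, and SAP 5.3 removes a participant from the immunogenicity evaluable population (IEP) when the deviation is judged exclusionary. Withdrawal from the study adds nothing to the analysis, and it ends the scheduled collection of safety data.

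The protocol treats a comparable case differently. Under 3.4.1.1, if a participant is unblinded, "the participant will be requested to remain in the study for safety follow-up". A noncompliant participant has no equivalent provision.

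At stake is the Day 183 incidence of SAEs, MAAEs and AESI, which serves a coprimary objective (Protocol 2.2). A crude percentage counts time nobody observed as time without an event, so incidence is understated. The understatement grows if those withdrawn are more likely than others to have events. The reason list in 4.3.5 also has no entry for withdrawn consent, although 4.3.1 is devoted to it, and none for noncompliance. The disposition table by arm (Protocol 9.6.1.1, SAP 7.1) therefore could not show how many withdrawals were avoidable.

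**Working it through.** **1. The sections side by side**

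| Question | Answer in the documents |
|---|---|
| Can a dosed participant be withdrawn for noncompliance? | Yes (Protocol 4.3.2) |
| Is safety follow-up intended for all? | Yes (Protocol 3.2.11, 4.3.2, 4.3.5) |
| What contact is scheduled after withdrawal? | The EDV only (4.3.3, 6.7, 3.9) |
| Are events up to and at the EDV counted? | Yes, and known events are followed (8.4, 8.4.2) |
| Are new events between the EDV and Day 183 collected? | Nothing schedules it |
| Does the person stay in the Day 183 denominator? | Yes (SAP 5.3, 9.2.1) |
| Is there a person-time or time-to-event method, or a rule for unobserved safety time? | No |

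The intention to follow everyone and the mechanism for withdrawn participants do not match.

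**2. Figures available**

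The plan gives no withdrawal rate. Its nearest figure is the 10% nonevaluable allowance (Protocol 9.1): 200 × (1 − 0.10) = 180 per arm, as stated. That allowance concerns immunogenicity. Here 10% serves only as the upper end of an assumed range.

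**3. Size when withdrawal is unrelated to events**

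Let I be true Day 183 incidence, w the fraction withdrawn and t the days from dose to withdrawal. Assume a constant hazard λ = −ln(1 − I)/182 and no contact afterwards. Then

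observed = (1 − w)·I + w·(1 − exp(−λt)).

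Example: I = 10%, w = 5%, t = 28 (Day 29). λ = 0.10536/182 = 0.000579, and 1 − exp(−0.01621) = 0.01608. Observed = 0.95 × 0.10 + 0.05 × 0.01608 = 0.0958. Missed per arm = 200 × 0.0042 = 0.84.

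| True I | w | Observed, Day 29 | Missed per 200 | Observed, Day 92 | Missed per 200 |
|---|---|---|---|---|---|
| 2% | 1% | 1.98% | 0.03 | 1.99% | 0.02 |
| 2% | 10% | 1.83% | 0.34 | 1.90% | 0.20 |
| 10% | 5% | 9.58% | 0.84 | 9.76% | 0.49 |
| 10% | 10% | 9.16% | 1.68 | 9.51% | 0.97 |
| 20% | 5% | 19.17% | 1.66 | 19.53% | 0.94 |
| 20% | 10% | 18.34% | 3.33 | 19.06% | 1.89 |

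For w from 1% to 10%, the relative understatement runs from about 0.5% to 8.4%.

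**4. Unequal withdrawal between arms**

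With I = 10% in both arms, and 5% against 1% withdrawn at Day 29, a spurious difference of 0.34 percentage points appears.

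**5. Withdrawal related to events**

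With uncommon events, withdrawal times uniform over follow-up, and an event rate r times higher in those withdrawn:

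relative shortfall = (r·w/2) / ((1 − w) + r·w).

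- r = 1: 1.0%, 2.5% and 5.0% for w = 2%, 5% and 10%.
- r = 3: 0.03/1.04 = 2.9%, 0.075/1.10 = 6.8% and 0.15/1.20 = 12.5%.

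The value r = 3 is illustrative; nothing in the documents supports a particular ratio.

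**6. The avoidable part**

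Steps 3 to 5 count every withdrawal. If, for illustration, half were for noncompliance, with the same timing and event rate as the rest, the change could recover at most 0.84 × 0.5 = 0.42 participants per arm in the example of step 3.

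**The case against.** A fair opponent would make five points.

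- **The intent is already written.** Sections 3.2.11, 4.3.2 and 4.3.5 all want safety follow-up for everyone. This stands as intent. But 4.3.2 sends the reader to 4.3.3, which provides only the EDV, so a site following the text has no later contact to make.
- **Withdrawn participants are not counted as event-free.** A reader might infer that they are. The documents do not support that: events up to and at the EDV are counted, and known events are followed under 8.4 and 8.4.2. Only the unobserved remainder is affected. Loss to follow-up is declared only after the projected last visit, so it does not itself cut contact short.
- **The Day 22 titer is not simply lost.** A reader might infer that it is. An EDV before Day 22 follows the Visit 3 or Visit 4 schedule, both of which include the neutralizing antibody draw. SAP 6.5.3 keeps out-of-window Day 22 results in the mITT population and adds nonresponder and last-observation-carried-forward analyses for missing ones. What remains is that an early sample or an imputed value may replace a Day 22 titer that could have been obtained.
- **Noncompliance still has a meaning.** Section 9.6.3 concerns treatment compliance, whereas 5.3 requires compliance with protocol and procedures to be monitored. This is correct. The point is that such noncompliance is no reason to end safety follow-up.
- **The consequence is limited.** Investigators are blinded (3.4.1), and safety endpoints are reported without formal testing (9.4.2), so no success criterion is touched. This stands too.

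**Conclusion.** The point holds in a narrow form. The protocol permits withdrawal for noncompliance after the only dose. It then schedules no collection of new SAEs, MAAEs or AESI beyond the EDV, contrary to 3.2.11 and to the stated intent in 4.3.2. In the crude Day 183 percentages, the unobserved time is treated as event-free.

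Under the assumptions in the working, the understatement is about 0.5% to 8.4% in relative terms when withdrawal is unrelated to events, and up to 12.5% in the illustrative threefold case. In counts, the calculated cases where withdrawal is unrelated to events miss between 0.02 and 3.33 participants with an event per 200. The withdrawal rates, event rates, timing and rate ratio are all assumed. The figures cover all withdrawals, so they are upper limits on what the change can recover.

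A reader might go further and conclude that discretionary withdrawal should be removed altogether, including under 8.4.2, which says: "Withdrawal of participants from the study to treat SAEs/AESI is at the discretion of the treating PI". The documents do not support that step. Withdrawal on health or best-interest grounds is a clinical judgment and is left as it is. The change is still worth making, because it is cheap and protects a safety endpoint that serves a coprimary objective.

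**What to change.** - **Protocol 4.3.2 and 4.3.3:** state that, once the investigational product has been given, noncompliance or a protocol deviation alone does not end follow-up. With the participant's agreement, the remaining blood draws continue. If these are declined, the Day 29, Day 92 and Day 183 contacts for SAEs, MAAEs and AESI are made by telephone. The deviation is recorded and handled through IEP membership.
- **Protocol 4.3.5 and the eCRF:** add withdrawal of consent and noncompliance as separate reasons.
- **SAP:** summarize duration of safety follow-up by arm next to the Day 183 incidence tables.
- **Unchanged:** the health-based and best-interest grounds in 4.3, 4.3.2 and 8.4.2 remain with the investigator.

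The cost is protocol wording, two eCRF codes, one summary of data already collected and a few extra telephone contacts. No additional participants are needed.
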